PROTOCOL NARRATIVE FOR EXPEDITED OR FULL COMMITTEE RESEARCH

University of California, Irvine Institutional Review Board Version: April 2013

HS#: 2015-2010
For IRB Office Use Only

Lead Researcher Name: [name]

Study Title: Pilot Study of Percutaneous Posterior Tibial Nerve Stimulation for the Treatment of Interstitial Cystitis/Painful Bladder Syndrome

NON-TECHNICAL SUMMARY

Provide a non-technical summary of the proposed research project that can be understood by IRB members with varied research backgrounds, including non-scientists and community members. The summary should include a brief statement of the **purpose of the research** and **related theory/data supporting** the intent of the study as well as a brief description of the **procedure(s) involving human subjects**. ***This summary should not exceed ½ page.***

Painful Bladder Syndrome (previously known as Interstitial Cystitis) is a long-lasting condition with symptoms of bladder pain (particularly when the bladder is full) and other bladder symptoms, such as frequent urination. No one knows the exact cause of painful bladder syndrome, but there are many theories and there are likely multiple factors that can lead to the same symptoms. Unfortunately, no cure for painful bladder syndrome has been found and most current treatments simply focus on improving symptoms.

The American Urological Association represents urologists who treat bladder conditions, and this society has published guidelines for doctors who treat Painful Bladder Syndrome. The guidelines suggest sacral neuromodulation as a 4th line treatment; sacral neuromodulation involves a two stage surgical procedure and the implantation of a permanent electrode and battery. Although the guidelines note that we do not know exactly why sacral neuromodulation improves the symptoms of Painful Bladder Syndrome, it is thought to affect the way pain signals from the bladder are sent to the brain.

Percutaneous posterior tibial nerve stimulation (PTNS) has more recently been approved for neuromodulation aimed at the same targets as sacral neuromodulation, without the need to have surgery or a permanently implanted device. The purpose of our research is to determine if PTNS is potentially helpful in the treatment of Painful Bladder syndrome. If this study suggests that PTNS is effective in treating symptoms, we believe additional research in this area will be worthwhile.

Our study will involve enrolling patients with Painful Bladder Syndrome and urinary frequency or urgency symptoms to treatment with 12 weekly treatments of PTNS. Each PTNS session involves placing a small needle (like an acupuncture needle) behind the inside of the ankle and connecting it to a mild electrical stimulation for 30 minutes. We will assess symptoms and bladder function before and after the treatments. At the end of the trial, patients will be asked to enroll (if they want to) in a continuation of the study to find out the duration of symptom improvement, if any is found.

PTNS is an FDA-approved treatment, and this study will involve only using PTNS for approved indications. The patients who participate in the study would be eligible to receive PTNS therapy as part of routine care. The study will involve the collection of additional information (in the form of questionnaires and voiding diary) on the subset of Painful Bladder Syndrome patients to learn how PTNS treatment affects their symptoms.

SECTION 1: PURPOSE AND BACKGROUND OF THE RESEARCH

1. Describe the **purpose of the research** project and state the overall objectives, specific aims, hypotheses (or research question) and scientific or scholarly rationale for performing the study.
2. Provide the **relevant background information** on the aims/hypotheses (or research question) to be tested and the procedures/products/techniques under investigation.
3. Include a description of the **primary outcome variable(s), secondary outcome variables, and predictors** and/or comparison groups as appropriate for the stated study objectives.
4. Include a critical evaluation of **existing knowledge**, and specifically identify the information gaps that the project intends to address.
5. Describe **previous research** with animals and/or humans that provides a basis for the proposed research. **Include references/citations**, as applicable.

This section should not exceed 4 pages.

1- Purpose of the research:

The objective of this prospective, pilot study is to determine if patients with urinary urgency, frequency and bladder pain also known as interstitial cystitis/painful bladder syndrome (IC/PBS) respond to percutaneous tibial nerve stimulation (PTNS) like patients with urinary frequency and urgency without pain. The specific aim is to evaluate how patients with IC/PBS respond to PTNS with regards to the reduction of symptoms in subjects with this disorder. Pre and post treatment questionnaires will be used to assess this endpoint.

The hypothesis is that subjects who receive PTNS will demonstrate a response to treatment through a reduction in symptoms similar to what has been described has been demonstrated in the literature with sacral neuromodulation (SNM) for IC/PBC. Though there is no uniform outcome measure for SNM studies, the majority use pain or symptom scales and have reported 55-80% response rates.¹ The study will assess response to PTNS treatment based on the variables described in section 3.

There is compelling scientific and scholarly rationale to perform this trial. Previous studies have found that PTNS may be helpful in chronic pelvic pain conditions but there are still many gaps in our knowledge regarding when and how effective this modality is. There are very few studies specifically examining PTNS in subjects with IC/PBS. Given how persistent and debilitating IC/PBS can be, even with the most thorough and advanced treatments, the potential to add another treatment modality with minimal morbidity to the treatment algorithm is significant.

2- Relevant background information:

IC/PBS is a chronic condition which is “characterized by an unpleasant sensation (pain, pressure, discomfort) perceived to be related to the urinary bladder, associated with lower urinary tract symptoms of more than six weeks duration, in the absence of infection or other identifiable causes.”² The most common lower urinary tract symptom is urinary frequency, often consequent to pain associated with bladder filling. Treatment for IC/PBS is often multimodal with behavioral modifications recommended first, followed by oral or intravesical medications and directed physical therapy. As a chronic pain condition, patients often require trials of multiple treatment modalities to manage symptoms or require chronic pain medication. Given that the etiology of IC/PBS is unknown, treatment currently focuses on managing symptoms, predominantly the complaints of pain and urinary frequency. Current treatment for refractory IC is often surgical/procedural and associated with significant cost and morbidity. Considerable benefit could be derived from contributing an additional treatment modality to the algorithm for IC/PBS.

Sacral neuromodulation (SNM) is fourth line treatment as outlined in the algorithm in the guidelines for diagnosis and treatment published by the American Urological Association in June 2011². The majority of the evidence supporting SNM in the treatment of PBS/IC comes from small case series of patients with refractory IC/PBS.¹ PTNS (under the brand name NURO™ System) is an FDA-

approved device for the treatment of urinary urgency, urinary frequency and urge incontinence. It is often described as a peripheral form of neuromodulation (as opposed to SNM which is central neuromodulation at the level of the nerve root). PTNS involves 12 weeks of weekly 30 minute office-based treatment sessions with a small electrode placed slightly above the ankle in order to stimulate the S2-4 nerve roots. If benefits are obtained, 12 weeks of treatment is followed by spaced maintenance sessions at timing of provider and patient discretion. In comparison, sacral neuromodulation (SNM) involves a two stage procedure, with both stages most often being performed under conscious sedation in the operating suite and leading to the implantation of a permanent device with consequent expense and risks. Because PTNS and SNM share some of the same mechanisms of action and are approved for treatment of some of the same indications, there has been interest in the utility of PTNS in the treatment algorithm of IC/PBS. Given that PTNS has FDA approval for the indication of urinary frequency, one of the most common complaints in IC/PBS, the majority of IC/PBS patients already qualify for PTNS. It is the objective of our trial to systematically study the utility of PTNS in IC/PBS.

Prior studies have examined PTNS for the treatment of a variety of pain syndromes. These studies have either been performed as single arm studies or with a comparison arm of routine care for IC/PBS.³ During literature search, we found only a single study that examined PTNS for treatment of IC/PBS and it only evaluated a highly refractory population with longstanding disease.⁴ Given the lack of literature and limited statistical information on which to base our estimates, it is beneficial to conduct a pilot study to collect additional information and direct future research.

3- Outcomes:

The primary outcome variable will be the percentage of subjects to report that they are moderately improved or markedly improved in overall symptoms compared to baseline on a 7-point global response assessment (GRA) scale. The GRA scale involves asking the question, "As compared to when you started the current study, how would you rate your overall symptoms now?". There are 7 possible responses: markedly worse, moderately worse, slightly worse, the same, slightly improved, moderately improved and markedly improved. This scale is the current standard for outcome in studies that are evaluating treatments and interventions for IC/PBS.

There will be a number of secondary outcome variables including: changes in a 24 hour voiding diary during the course of the interventions, ratings for bladder pain, urinary urgency and urinary frequency on standardized scales, the score on O'Leary-Sant IC Symptom and Problem Index, scores validated questionnaires for pelvic floor, sexual dysfunction and general health and any reports of adverse events.

The study will also examine demographic data and information on the course of the disease in subjects.

4- Existing Knowledge:

There are few published studies looking at PTNS and IC/PBS. Literature review identified six studies that evaluated the effect of PTNS on pain syndromes. Four of these studies looked at chronic pelvic pain^{5,6,7,8}, one study evaluated chronic prostatitis/chronic pelvic pain in men⁹ and only a single study examined PTNS in patients with IC/PBS¹⁰. However, in the study of IC/PBS, there was a nonstandard treatment course (10 instead of 12 sessions of PTNS), the subjects had severely refractory IC/PBS with multiple prior treatments attempted in all cases and often long-standing disease (up to 22 years). By only examining highly refractory subjects, the potential benefit of a minimally invasive intervention early in the disease process may have been missed.

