Treatment (Visits 7-11): Prior to the start of seventh treatment visit, the subject will return the additional forms/questionnaires. These visits will continue to be conducted in the UCI urogynecology clinic. PTNS will be administered by a clinical nurse under physician supervision. This is standard of care in clinical practice. Treatments will be administered per standard protocol. At all visits, the nurse will inquire regarding any noted adverse reactions to treatment and will have the subject complete a VAS.

Each treatment takes approximately 30 minutes.

Final Treatment (Visit 12): This visit will be conducted per the routine protocol in visits 1-11, with any adverse reactions noted and a VAS collected. After completion of the visit, the patient will be given the following materials for completion within the subsequent two weeks.

a) 7-point global response assessment (GRA) scale

b) 24 hour voiding diary

c) visual analog scale (VAS) for bladder pain

d) Pelvic Pain and Urgency/Frequency Patient Symptom Scale (PUF Questionnaire)

e) O'Leary-Sant IC Symptom and Problem Index

The time required for the treatment session and completion of the forms is 45 minutes.

Follow-up (Visit 13): This visit will consist of a follow-up clinic visit with the subjects' provider per routine care. If not returned previously, the patient will submit the materials completed after Visit 12. The subject and her provider will review her current symptoms and complaints and create an individualized management plan. At this time, depending on their current symptoms and response to the treatment, the subjects will be offered to continue with PTNS treatments at a standard maintenance interval (typically every 4-6 weeks) or to pursue alternative care outside of the study protocol if no benefit was obtained from treatment. Any additional treatments (PTNS or otherwise) after the 12 sessions of PTNS are not considered part of the study and will be determined by provider and patient per clinical standard of care. At this time, we will offer patients to enroll in post-study follow up. If they choose to continue, they will have a visit 14.

This visit will require 30 minutes.

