Post-study Follow-Up (Visit 14) - optional: This visit will occur 12-16 weeks after the last treatment visit and will consist of providing the subject with additional surveys to monitor progression of symptoms and maintenance of potential benefits. The subject will be encouraged to complete these materials through the method of contact she prefers. The following materials will be administered:

a) 7-point global response assessment (GRA) scale

b) 24 hour voiding diary

c) visual analog scale (VAS) for bladder pain

d) Pelvic Pain and Urgency/Frequency Patient Symptom Scale (PUF Questionnaire)

e) O'Leary-Sant IC Symptom and Problem Index

f) Post-study follow-up survey

The forms will take 20 minutes to complete and the 24 hour voiding diary will require approximately 20 minutes spread throughout 1 day.

Study design-

This a single-arm pilot study.

Study endpoints-

The end point for initial evaluation of data is following 12 treatment weekly treatment sessions of PTNS and completion of a 24 hour voiding diary and repeat surveys. At this time, depending on their current symptoms and response to the treatment, the subjects will be offered to continue with PTNS at maintenance intervals or pursue care outside of the study protocol. We will offer patients to enroll in

post-study follow up as described previously.

All treatment visits will take place in the UCI urogynecology clinic. Enrollment and follow-up visits may take place in the clinic or over the phone if the subject prefers this method of contact.

2. Routine medical procedures:

This study involves a standard of care medical procedure/intervention that will be administered in the standard fashion and frequency as they are performed in non-research settings. The device will not be used concurrently with other medical monitoring equipment and that it will not be used in or around water.

PTNS involves the placement of a thin needle (similar to an acupuncture needle) inserted near the posterior ankle. The needle is then connected to an electrode stimulator and the stimulation is adjusted until appropriate response (toe flex or fan) is obtained without patient discomfort. When at the appropriate level, the electrode is stimulated for 30 minutes per treatment session. The most frequent adverse reaction to PTNS is a small, temporary local reaction (inflammation or pain) at or near the site of needle insertion. (See image below for location of needle insertion; arrow is pointing to device.)

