While subjects will be restricted from receiving new additional standard therapies during the course of the study, there is very limited risk associated with this because they will only be restricted during the course of the study protocol. Patients will be permitted to continue standard of care oral medical therapies (such as pyridium, Elmiron, or other medications considered second line in the AUA guidelines for treatment of IC/PBS) if they had been receiving this medication prior to enrollment in the trial protocol. If they so choose, they will be able to receive any other additional indicated treatments immediately following conclusion of the trial protocol. If they choose to withdraw from the study in order to receive another indicated (standard) therapy that will be noted and included in our results. Any subject who withdraws will be offered an appointment with her physician.

PHI will be collected as part of this study. Breach of confidentiality is a theoretical risk.

5. Discuss what steps have been taken and/or will be taken to **prevent and minimize** any risks/ potential discomforts to subjects (address physical risks as well as other risks such as the potential for a breach of confidentiality). Examples include: designing the study to make use of procedures involving less risk when appropriate; minimizing study procedures by taking advantage of clinical procedures conducted on the subjects; mitigating risks by planning special monitoring or conducting supportive inventions for the study.

All subjects will be carefully monitored throughout the study protocol. They will have weekly visits with a trained, urogynecology practitioner who will be administering the PTNS treatments. This provider is qualified to assess and triage complaints related to the PTNS procedure and will contact the appropriate research physician if additional assessment is indicated. The practitioner administering the PTNS treatments will work with the subject, in the standard fashion for PTNS, to minimize any transient discomfort during the treatments.

Subjects may return to UCIMC urogynecology clinic for additional visits outside of the study protocol at their own discretion, if there are any complaints they feel need to be assessed by a physician. We will work to minimize inconvenience associated with study participation by allowing the subject to schedule the PTNS treatments at the time most convenient for them, within clinic scheduling ability.

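### Can a single optional visit at 12 to 16 weeks deliver the duration of improvement that the lay summary mentions?

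*Combined protocol and SAP*

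**What the plan says.** The Non-technical summary tells IRB members that patients may join a "continuation of the study to find out the duration of symptom improvement, if any is found".

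Section 3A (chronological description and visit table) sets out what that extension contains. There is one optional contact, Visit 14. On timing: "This visit will occur 12-16 weeks after the last treatment visit". Its content is "additional surveys to monitor progression of symptoms and maintenance of potential benefits": the GRA, the 24-hour diary, the VAS, the PUF, the O'Leary-Sant indices and a post-study follow-up survey. On the mode of completion: "The subject will be encouraged to complete these materials through the method of contact she prefers".

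Enrolment in the extension is offered at Visit 13, when response is reviewed. At that visit "the subjects will be offered to continue with PTNS treatments at a standard maintenance interval (typically every 4-6 weeks"), or they may seek alternative care if they had no benefit. The protocol adds: "Any additional treatments (PTNS or otherwise) after the 12 sessions of PTNS are not considered part of the study". Section 7B says that after the trial protocol ends "they will be able to receive any other additional indicated treatments immediately following conclusion of the trial protocol".

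Section 1 (Outcomes) names the GRA responder percentage as primary and a list of symptom measures as secondary. Duration of response is not among them. Section 3B plans a responder proportion with 95% limits and paired comparisons of baseline with follow-up. It mentions neither Visit 14 nor duration.

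**The concern.** Duration of benefit is a time. Measuring it needs either repeated assessment or a dated report of when symptoms came back. The extension as described has one assessment, chosen by patients who already know whether they improved, and it falls after an interval in which care is unrestricted. A patient still improved at Visit 14 could owe that to the 12 sessions, to later PTNS or to another therapy.

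If the lay sentence were taken as the aim, a report might present persistence under mixed care as the lasting effect of the 12-session course. Anyone planning a later trial or a maintenance schedule could be misled. Interim therapy, if not recorded at Visit 14, may also be hard to recover afterwards.

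**Working it through.** The plan gives no duration figure to reproduce, so the check sets the texts side by side and works out what Visit 14 can show.

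**1. Which text governs.** The duration wording stands only in the Non-technical summary, which the form limits to half a page for a mixed readership that includes non-scientists. The procedural text in Section 3A speaks of progression and maintenance. Sections 1 and 3B contain no duration aim, outcome or analysis. No planned output would therefore carry a duration claim.

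**2. Timing.** The last treatment visit is read as Visit 12, because later treatment is outside the study. Patients receive the Visit 12 forms as "materials for completion within the subsequent two weeks", so that assessment lies at weeks 0 to 2. Visit 14 lies at weeks 12 to 16.

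- Shortest gap: 12 − 2 = 10 weeks
- Longest gap: 16 − 0 = 16 weeks

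The GRA asks about present symptoms relative to study start, so it gives status and not the date of a change.

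**3. Further PTNS before Visit 14.** For a patient who accepts maintenance, whole sessions counted from Visit 12 are:

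| Visit 14 at | Every 6 weeks | Every 4 weeks |
|---|---|---|
| week 12 | 12/6 = 2 | 12/4 = 3 |
| week 16 | 16/6, so 2 | 16/4 = 4 |

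If a session in the same week as Visit 14 is left out, the smallest count falls to 1. Counted instead from a Visit 13 assumed at week 2 (its date is not given), the range is 1 (week 8) to 3 (weeks 6, 10 and 14). A patient who declines has 0.

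**4. What Visit 14 does show.** Pairing the Visit 12 and Visit 14 forms gives the proportion of returning responders who are still responders. For a responder with no interim therapy, it also gives coarse duration information. Still improved means that response was present at 12 to 16 weeks (right-censored). No longer improved means that it was lost somewhere in the 10 to 16 week gap (interval-censored). The other scales can be compared directly between the two time points. This matches the purpose stated in Section 3A.

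**5. What extra reporting would add.** One could split Visit 12 responders by interim therapy: none, maintenance PTNS, other. The protocol's own example in Section 4A, 60% of 24, gives 24 × 0.60 = 14.4, or about 14 responders. Three groups would hold 14/3, or about 5 each, and that assumes everyone returns. With 4 of 5 sustained, the exact (Clopper-Pearson) 95% interval is 28.4% to 99.5%. Even unsplit, 7 of 14 has an exact interval of 23.0% to 77.0%. The split would also be confounded, because the therapy chosen at Visit 13 depends on the response seen there.

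**The case for a change.** The best case for a change is that it costs almost nothing. One sentence could be reworded to match Section 3A, the survey could be checked for items on PTNS sessions and new therapies since Visit 12, and a short descriptive paragraph could be promised. The lay summary is what non-scientist IRB members read, and it is the only place that states the extension's aim as duration. The attribution problem is genuine, since steps 2 and 3 show that Visit 14 alone cannot isolate the lasting effect of the 12 sessions.

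What stands is the difference in wording and the limit on interpretation. The rest does not carry a change:

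- Rewording a lay sentence alters nothing that the trial does, analyses or concludes.
- The survey is listed for Visit 14, and Section 3A says the instruments are attached. Its items are not in the text available, so nothing shows that interim therapy goes unrecorded.
- The added reporting is a confounded description in cells of about five, for an analysis that the plan never undertook to provide.
- The summary speaks of duration of improvement, not of duration without further treatment. Section 1 describes spaced maintenance sessions as the usual sequel when there is benefit, so persistence under usual care is a fair lay reading.

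**Conclusion.** The concern does not call for a change. The lay sentence is looser than the procedure it summarises, but the procedure is stated correctly where it governs. Visit 14 supports a statement about persistence of response at 12 to 16 weeks under usual care among those who return. It does not support a dated duration of the 12-session effect, unless the survey dates symptom return. An analyst working from Section 3A would report it that way.

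The effect on the primary result is nil, because the GRA proportion after 12 sessions uses no Visit 14 data. For the extension, the limit is a 10 to 16 week window for any loss of response, with between 0 and about 4 further PTNS sessions inside it.

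This rests on two assumptions: that the last treatment visit means Visit 12, and that the analysis after the intervention uses the forms issued at Visit 12. The Visit 14 return rate is not given, and the conclusion does not depend on it.

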Screening: Once consents have been signed, the patients will be assessed by the MD for participation and screened to confirm they meet inclusion and exclusion criteria.

The screening will take approximately 20 minutes, not including routine care.

Pre-treatment (Visit 0): This visit will follow the screening visit. The following materials will be given and tests will be administered:

- a) demographic and history survey
- b) 24 hour voiding diary
- c) visual analog scale (VAS) for bladder pain
- d) Pelvic Pain and Urgency/Frequency Patient Symptom Scale (PUF Questionnaire)
- e) O'Leary-Sant IC Symptom and Problem Index
- f) urine pregnancy test (for all premenopausal subjects)

Questionnaires will be provided and will take 20 minutes to complete. The 24 hour voiding diary will be sent home with the patient and will require approximately 20 minutes spread throughout 1 day.

Treatment (Visits 1-5): Prior to the start of first treatment visit, the subject will return the above forms/questionnaires. These visits will be conducted in the UCI urogynecology clinic. PTNS will be administered by a clinical nurse under physician supervision. This is standard of care in clinical practice. These treatments will occur weekly for 12 weeks total. Treatments will be administered per standard protocol. At all visits, the nurse will inquire regarding any noted adverse reactions to treatment and will have the subject complete a VAS.

Each treatment takes approximately 30 minutes.

Treatment (Visits 6): This treatment visit will be administered in the same fashion and with the same requirements as all other treatment visits. Following this visit, the subject will be provided with the following forms/questionnaires to complete prior to the subsequent visit:

- a) 7-point global response assessment (GRA) scale
- b) 24 hour voiding diary
- c) visual analog scale (VAS) for bladder pain
- d) Pelvic Pain and Urgency/Frequency Patient Symptom Scale (PUF Questionnaire)

e) O'Leary-Sant IC Symptom and Problem Index

The time required for the treatment session and completion of the forms is 45 minutes.

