This is a pilot study with primary aim to estimate the proportion of patients experiencing moderate or marked improvement in overall symptom score as measured by response to a 7-point global response assessment scale collected after the intervention period. Responders will be defined as those reporting a moderate or marked improvement in symptoms in global response score. We will estimate the proportion of responders with 95% confidence limits, as defined by a response of moderate or marked improvement on the GRA scale collected at follow-up. Pain response will be measured using the Pelvic Pain and Urgency/Frequency Patient Symptom Scale (score total range: 0-35). We will estimate mean (plus standard deviations and 95% CI) for pain score at baseline and follow-up and change in response to therapy, testing for change over time using a paired t-test.

Other secondary outcomes that we will be reviewing are: change in frequency of urinary collected in 24 hour voiding diaries, change in visual analog scale, and change in O'Leary-Sant IC Symptom and Problem Index. These data consist of continuous variables to be described using means, SDs and confidence intervals at baseline and follow-up. Change over time will also be estimated and tested for difference from zero using a paired t-test.

SECTION 4: SUBJECTS (PERSONS/CHARTS/RECORDS/SPECIMENS)

A. Number of Subjects (Charts/Records/Biospecimens)

- Indicate the **maximum number of subjects to be recruited/consented** on this UCI protocol. This is the number of potential subjects you may need to recruit to obtain your target sample size. This number should include projected **screen failures and early withdrawals**. *Note: The IRB considers individuals who sign the consent form to be "enrolled" in the research.*
- For **Mail/Internet surveys** include the number of people directly solicited.
- If the study involves use of **existing charts, records, biospecimens**, specify the maximum number that will be reviewed/tested to compile the data or the sample population necessary to address the research question.

32

- Of the maximum number of subjects listed above, indicate the **target sample size** for the study. This is the number of subjects expected to complete the study or the number necessary to address the research question.

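### The forms collected after Visit 6 enter no planned estimate, and the two-point paired t-test drops women who return them but miss the post-Visit 12 forms

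*Combined protocol and SAP*

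**What the plan says.** **Outcome.** Section 1, item 3 (Outcomes) includes among the secondary outcomes "changes in a 24 hour voiding diary during the course of the interventions".

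**Collection.** The chronological description of study activities says of Visit 6: "Following this visit, the subject will be provided with the following forms/questionnaires to complete prior to the subsequent visit". The list opens with "a) 7-point global response assessment (GRA) scale" and continues with the 24-hour diary, a VAS, the PUF and the O'Leary-Sant index. Under Visits 7-11: "Prior to the start of seventh treatment visit, the subject will return the additional forms/questionnaires". The visit table repeats the Visit 6 list. The same forms are issued after Visit 12 and at the optional Visit 14.

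**Analysis.** Section 3B estimates one responder proportion, "as measured by response to a 7-point global response assessment scale collected after the intervention period", and repeats the definition as "as defined by a response of moderate or marked improvement on the GRA scale collected at follow-up". PUF is summarised at baseline and follow-up, with change tested by a paired t-test. Diary frequency, VAS and O'Leary-Sant are to be "described using means, SDs and confidence intervals at baseline and follow-up", again with a paired t-test of change. Section 3B does not tie the word follow-up to a visit number.

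**Withdrawal.** Section 4A allows for 33.3% exclusion or withdrawal. Section 7B foresees women leaving to receive another standard therapy and says this will be noted and included in the results.

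**The concern.** Subjects complete a full set of instruments at mid-course, including the primary one, and the plan gives the results no use. Two things are at stake.

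1. **Time course.** A pilot meant to direct further research would gain from reporting whether response is visible after 6 sessions, and whether it grows or fades by 12. Without a planned estimate, any Visit 6 result that is reported will have been chosen after the data were seen.
2. **Who is analysed.** A paired t-test needs both readings. A woman who returns the Visit 6 forms and stops before the post-Visit 12 forms contributes nothing to the mean change in diary, PUF or O'Leary-Sant. If women who are doing poorly are more likely to leave, the mean among those who stay looks too favourable.

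The point concerns the Visit 6 forms. The VAS is also recorded at every treatment visit and is not part of the argument.

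**Working it through.** **Step 1. Collection set against analysis.**

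| Instrument | Scheduled readings | Readings used in Section 3B |
|---|---|---|
| GRA | after Visit 6, after Visit 12, optional Visit 14 | one, at follow-up |
| Diary, PUF, O'Leary-Sant | Visit 0, after Visit 6, after Visit 12, optional Visit 14 | two, baseline and follow-up |

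Section 3B does speak of change over time, but attaches the phrase to a paired t-test, which compares two readings, and names only two. No section assigns the Visit 6 forms to an estimate, model or table.

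**Step 2. The plan's own figure.** Section 4A states ±0.2 at n = 24. The Wald half-width is 1.96 × √(p(1−p)/n). At p = 0.6 this is 1.96 × √(0.24/24) = 1.96 × 0.100 = 0.196, giving 0.404 to 0.796. The figure reproduces. It covers only the follow-up GRA and is not in dispute.

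**Step 3. Precision of a Visit 6 responder proportion.** The same formula applies; the rates and return counts are assumptions.
- n = 24, rates from 20% to 60%: half-width from 1.96 × √(0.16/24) = 0.160 up to 0.200 (the maximum, at 50%).
- n = 18, same rates: 0.185 to 0.231.

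The added estimate would be about as precise as the primary one and needs no more subjects.

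**Step 4. Who supplies Visit 6 data.** The forms are handed out after Visit 6 and returned at Visit 7. A woman who stops straight after session 6 has no scheduled return route. The recoverable women are those who reach Visit 7 and stop later.

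**Step 5. Possible size of the completer bias.** The documents give no SD, correlation or dropout mechanism, so all of these are assumed: true mean change −5 points, SD 6, correlation 0.7 between Visit 6 and Visit 12 change, and dropout odds ratio 2.7 to 4.5 per SD of worse Visit 6 change. The 32 in Section 4A is the consented maximum and includes screen failures, so 32 treated is an upper bound. A milder case is 28 treated with 4 lost (4/28 = 14%), which leaves the target of 24. Simulated means, with overstatement = (|mean| − 5)/5:

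| Setting | Completer mean | Overstatement |
|---|---|---|
| 28 treated, 14% loss | −5.5 to −5.7 | 10-14% |
| 32 treated, 28% loss | −6.0 to −6.3 | 20-26% |
| Random dropout | about −5.0 | none |

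**Step 6. What a model using Visit 6 recovers** (32 treated, 28% loss):
- every dropout has returned the Visit 6 forms: about −5.0, bias removed;
- half of the dropouts have not: about −5.4 to −5.6, bias partly removed;
- no dropout has: same as the completer mean, no gain;
- dropout follows the Visit 12 outcome itself: about −5.8 to −6.1, bias remains.

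With random dropout at 25-30% loss, the only gain is precision: the standard error falls from about 1.24 to 1.16.

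**The case against.** **The diary outcome may simply mean before-to-after change.** Section 1 speaks of pre- and post-treatment questionnaires, the summary of assessment before and after treatment, and the study endpoints paragraph puts the evaluation after the 12 sessions. On that reading Section 3B does analyse the declared outcome. This stands. A reader might infer that a declared outcome is never estimated, but the documents support only the conditional statement: on the within-course reading, it is partly analysed. On either reading the Visit 6 forms are unused.

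**The Visit 6 responder rate is not a declared outcome.** This also stands. Section 1 names no such outcome and Section 3B places the GRA after the intervention period. Leaving it out contradicts nothing; it is an unassigned measurement of the primary instrument.

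**Mid-course scores do not exist for everyone who stops after session 6.** Correct, because the forms come back at Visit 7. It limits the benefit to later dropouts.

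**The bias figures are built on invented inputs.** Fair. The 33.3% in Section 4A combines exclusion with withdrawal, and nothing says when women leave. A reader might infer that the planned estimate is biased by a fifth or more and that a model would restore the truth; the documents support neither. They do support the expectation of withdrawal, including for another therapy. Section 7B's promise to include such withdrawals in the results has no counterpart for their scores in Section 3B.

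**Conclusion.** The point holds as a gap in pre-specification and in the use of collected data, worth correcting but of modest weight. GRA, diary, PUF and O'Leary-Sant data collected after Visit 6 have no planned use, and the two-point test discards women who return those forms and leave before the final ones. The bias in the secondary mean changes could be nil (random dropout), about 10-14%, or about 20-26%, under the assumptions in the working. The overstatement shrinks at lower correlations between the two visits. A model using Visit 6 removes that bias wholly, partly or not at all, depending on when and why women leave. The primary responder estimate, its confidence interval and the sample size of 24 are unaffected.

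**What to change.** In Section 3B:

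1. Define follow-up as the forms issued after Visit 12.
2. For diary frequency, PUF and each O'Leary-Sant index, replace the paired t-test with a repeated-measures model on Visits 0, 6 and 12 with unstructured covariance. Include every woman with a baseline and any later reading. Report change at Visit 6 and at Visit 12 with 95% confidence intervals.
3. Report the Visit 6 GRA responder proportion with its 95% confidence interval, labelled secondary and descriptive, and cross-tabulate it with the Visit 12 response.
4. In Section 1, say whether the diary outcome means within-course change or before-to-after change.

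**Cost.** Wording and a little programming; no new data, visits or subjects. With complete data and unstructured covariance, the Visit 12 change agrees with the paired comparison; a more restrictive covariance structure would alter its standard error. The price is a missing-at-random assumption, which should be stated. The model cannot recover women who stop before returning the Visit 6 forms, so the number with each set of forms should be reported.
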